## **6.6. Assessments for Early Discontinuation From Study Intervention or From the Study**

If a participant discontinues study medication dosing (eg, as a result of an AE), every attempt should be made to keep the participant in the study and continue to perform the required study-related follow-up and procedures ([Section 3.3](#)). If this is not possible or acceptable to the participant or investigator, the participant may be withdrawn from the study. The participant will be requested to return for an early study ESDD visit. If it is not possible or acceptable to the participant or investigator to keep the participant in the study (after discussion of the benefits/risks with the investigator), the participant may be withdrawn from the study and be required to return to the study site for a 30-day follow-up visit ([Table 3](#)).

### **6.6.1. Assessments for Early Discontinuation From Study Intervention**

A participant who discontinues study drug early will be asked to return to the investigational site within 72 hours of stopping study drug, or within 72 hours of notifying the investigator they no longer wish to receive study drug, to attend an ESDD visit for assessments and procedures specified in [Table 3](#).

### **6.6.2. Assessments for End of Study**

A participant who discontinues study drug early will be asked to return to the investigational site within 30 days of stopping study drug to attend an ESDD visit for assessments and procedures specified in [Table 3](#).

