### 11.3. Study Procedures Table

**Table 3. Study Procedures Table**

Study Procedures	Screening	Day 1 b	Week 4 c	Week 12 c	Week 24 c	30-Day Follow-up d	ESDD e	Notes
Informed Consent	X							
Medical History	X							
Concomitant Medications	X	X	X	X	X	X	X	At screening, concomitant medications taken within 30 days prior to screening will be recorded; at subsequent visits all medications since the last study visit will be recorded.
Adverse Events	X	X	X	X	X	X	X	
Complete Physical Examination	X							Complete physical examination (urogenital/anorectal examinations will be performed at the discretion of the investigator).
Symptom-Directed Physical Examination		X	X	X	X	X		Symptom-directed physical examination at all post-screening time points.
Vital Signs and Weight	X	X	X	X	X	X	X	
Height	X							
Urinalysis	X	X	X	X	X	X	X	
Urine Pregnancy		X	X	X	X	X	X	For participants of childbearing potential only
Serum Pregnancy	X							For participants of childbearing potential only
Chemistry Profile f	X	X	X	X	X	X	X	
Hematology Profile	X	X	X	X	X	X	X	CBC with differential and platelet count
CD4+ Cell Count	X	X		X	X		X	
Plasma HIV-1 RNA g	X	X	X	X	X	X	X	
HBV and HCV Serologies h	X							
Estimated GFR	X	X		X	X		X	Estimated GFR according to the Cockcroft-Gault formula for creatinine clearance
Metabolic Assessments i		X		X	X			
Baseline PK, Sparse PK: trough and postdose PK sample j		X	X	X	X			

Study Procedures	Screening	Day 1 b	Week 4 c	Week 12 c	Week 24 c	30-Day Follow-up d	ESDD e	Notes
Plasma Storage Sample		X	X	X	X		X	For optional future research
Whole Blood sample for potential HIV DNA genotyping		X						Whole blood sample for virology analysis
Plasma HIV-1 genotyping/phenotyping sample k			X	X	X		X	HIV-1 genotype/phenotype resistance testing for participants with unconfirmed virologic rebound with HIV-1 RNA value $\geq 200$ copies/mL
Dried Blood Spot (DBS) collection			X	X	X		X	TFV-DP from DBS will be run in retrospect for participants with confirmed viral failure.
HIVTSQs		X		X	X			
HIVTSc Questionnaire			X					
Additional study specific questions		X	X					
Qualitative interview			X					Qualitative interview will explore in-depth experiences on CAB+RPV, reasons for switch B/F/TAF and satisfaction post switch. The visit window for the interview is from Week 3 to Week 9.

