Study Drug Accountability		X	X	X	X	X	X	
Study Drug Dispensation		X		X				
Observed Dosing		X	X	X				Participants must take their study drug in the clinic for observed dosing on Day 1, Week 4, and Week 12.

CBC = complete blood count; CD4+ = clusters of differentiation 4; DNA = deoxyribonucleic acid; DBS = dried blood spot; ESDD = early study drug discontinuation; GFR = glomerular filtration rate calculated using the Cockcroft-Gault equation; HBV = hepatitis B virus; HCV = hepatitis C virus; HIV-1 = human immunodeficiency virus type 1; HIVTSQs = HIV treatment satisfaction status questionnaire [quantitative]; HIVTSQc = HIV treatment satisfaction change questionnaire [quantitative]; RNA = Ribonucleic acid; PK = pharmacokinetic(s); TFV-DP = tenofovir diphosphate.

- a Evaluations to be completed within 42 days prior to Day 1 visit.
- b Participants will be dispensed study drug at the Day 1 visit; initiation of treatment with the study drug must take place in the clinic for observed dosing at Day 1 visit.
- c All study visits are to be scheduled relative to the Day 1 visit date. Visit windows are  $\pm 2$  days of the protocol-specified date through Week 12,  $\pm 6$  days of the protocol-specified date for Week 24. For the purpose of scheduling a 30-day follow-up visit, a  $\pm 6$ -day window may be used. Those participants who prematurely discontinue study drug and continue in the study through at least one subsequent visit after the early study drug discontinuation visit will not be required to complete the 30-day follow-up visit.
- d Only applies to participants who miss the Week 24 visit, and must be completed within 30 days of discontinuing study drug.
- e Early study drug discontinuation visit to occur within 72 hours of last dose of study drug.
- f Chemistry profile: alkaline phosphatase, AST, ALT, total bilirubin, direct and indirect bilirubin, total protein, albumin, bicarbonate, BUN, calcium, chloride, creatinine, glucose, potassium, and sodium.
- g For any post-Day -1 visit, if the HIV-1 RNA value is  $\geq 50$  copies/mL, a retest should be performed at a scheduled or unscheduled visit 2-4 weeks after the date of the original test.

- h Hepatitis B virus surface Antigen (HBsAg), Hepatitis B core antibody (HBcAb), and Hepatitis C virus (HCV) serologies (reflex HCV RNA is performed in participants with positive HCV Ab serology)

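### Protocol Section 6.6.2 puts the early study drug discontinuation (ESDD) visit within 30 days of stopping drug, while Section 6.6.1, Table 3 and the SAP set it at 72 hours

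*Protocol*

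**What the plan says.** Two adjacent protocol subsections address the same people, participants who discontinue study drug early, and send them to a visit with the same name.

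- **Section 6.6.1** asks for the ESDD visit "within 72 hours of stopping study drug, or within 72 hours of notifying the investigator".
- **Section 6.6.2**, headed as assessments for end of study, asks for return "within 30 days of stopping study drug to attend an ESDD visit".

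Table 3 footnote e agrees with 6.6.1: "Early study drug discontinuation visit to occur within 72 hours of last dose of study drug". SAP Appendix 1 footnote e repeats it.

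The 30-day timing otherwise belongs to a different visit with its own Table 3 column. Section 6.6 ends by saying that, if a participant cannot be kept in the study, "the participant may be withdrawn from the study and be required to return to the study site for a 30-day follow-up visit". Footnote d says of that visit: "Only applies to participants who miss the Week 24 visit, and must be completed within 30 days of discontinuing study drug". Footnote c keeps the two visits apart: a participant who stays in the study for at least one visit after ESDD "will not be required to complete the 30-day follow-up visit".

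**The concern.** One named visit has two deadlines, 3 days and 30 days after stopping, for the same participants. ESDD is more than an administrative visit. Section 6.4 lists it as a form of last on-treatment visit. Section 6.4.1.1 counts HIV-1 RNA of 50 copies/mL or more at ESDD as virologic failure, and 200 copies/mL or more triggers resistance testing. Table 3 also schedules the dried blood spot at ESDD, which is used retrospectively for TFV-DP in confirmed failure.

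If these samples are taken weeks after the last dose, a rebound caused by stopping treatment could be recorded as failure of B/F/TAF, and the dried blood spot would no longer describe exposure at the time of stopping. The RNA result could also enter the windowed efficacy summaries.

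**Working it through.** The plan gives no figure to reproduce. The check compares the texts and adds simple date arithmetic.

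**1. Which element of 6.6.2 is wrong.** Its heading concerns end of study, Section 6.6 closes by naming a 30-day follow-up visit, and footnote d gives that visit the 30-day limit. Together these suggest that the timing is right and the visit name is wrong. The population was also carried over from 6.6.1, whereas footnote d confines the follow-up visit to participants who miss Week 24.

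**2. Possible delay.** The ESDD limit is 72 hours = 3 days. The 6.6.2 limit is 30 days.

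- Counted from the stop date: 30 - 3 = 27 days.
- Under the 6.6.1 alternative, with the investigator notified n days after stopping, the limit is n + 3 days and the excess is 30 - (n + 3) = 27 - n. As assumed examples, n = 7 gives 20 days and n = 14 gives 13 days.

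**3. Whether the two visits are interchangeable.** Table 3 marks five procedures at ESDD that it does not mark at the 30-day follow-up: CD4+ count, estimated GFR, plasma storage, genotype/phenotype sample and dried blood spot. HIV-1 RNA is marked at both. The symptom-directed examination is not a difference. Its ESDD cell is empty, but the row note reads "Symptom-directed physical examination at all post-screening time points" and Section 6.3.4 says the same.

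**4. Effect on windowed RNA.** SAP Section 6 includes efficacy data collected after the last dose, and SAP Section 3.7.4 selects the latest RNA record in a window. SAP Table 3-1 sets Week 12 at Days 57 to 126 and Week 24 at Days 127 to 210. The stop dates below are assumed.

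- *Stop on Day 90.* An ESDD visit at 72 hours falls on Day 93; at 30 days it falls on Day 120. Both lie in the Week 12 window, so the Day 120 value, taken off drug, would replace any earlier one.
- *Stop on Day 100.* At 72 hours the visit is on Day 103, in the Week 12 window. At 30 days it is on Day 130, in the Week 24 window. Week 12 then falls back on an earlier record, and Day 130 becomes the Week 24 value under missing = excluded if nothing later exists.

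In both cases the participant stopped after Day 57, so discontinuation = failure does not impute a Week 12 failure and the measured RNA decides. At Week 24 that method counts both as failures whatever the RNA, because they stopped before Day 127.

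**5. Whether the follow-up limit should move.** Footnote c allows 6 days either side "For the purpose of scheduling a 30-day follow-up visit", which on its own would reach 30 + 6 = Day 36 after stopping. Adverse event collection (Protocol 7.3.2) and the treatment-emergent laboratory definition (Protocol 8.6.3, SAP 7.3.2.1) end 30 days after the last dose. Results from Days 31 to 36 would fall outside. Footnote d's limit keeps the visit inside.

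**The case against.** The strongest reply is that 6.6.2 cannot be carried out alone. It lists no procedures and refers the site to Table 3, where the ESDD column carries the 72-hour footnote, and 6.6.1 sits directly above it. This stands as a reason to expect few errors. It does not remove the contradiction: a site trying to obey both subsections could hold ESDD at 72 hours and repeat it by Day 30.

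A second reply is that Section 6.4 and the heading of 6.4.1.1 speak of the last on-treatment visit, so a late sample should not count as failure. That is the better reading. But the failure rule in the body of 6.4.1.1 applies at ESDD without a time condition, so a late visit labelled ESDD could still be classified by it.

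Third, the 30-day follow-up visit also includes RNA, so off-drug values can enter the windows even when the visit is named correctly. That is true: the RNA effect is not unique to this sentence. The follow-up visit, however, is limited by footnotes c and d, whereas 6.6.2 as worded covers every early discontinuer.

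Fourth, some of the procedure difference carries little weight. Table 3 describes the plasma storage sample as being for optional research, and the SAP summarizes CD4 only to 1 day after the last dose. This stands, and the point rests on the RNA, resistance and dried blood spot samples.

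A reader might also infer that footnote d should be widened to match footnote c, or that footnote e must add the notification alternative from 6.6.1. The documents do not require either. The first would take visits past the 30-day safety period, and the second is a matter of preference.

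**Conclusion.** Section 6.6.2 is wrong as written, and the point is minor. ESDD sampling could be taken or repeated up to about 27 days after the 72-hour limit, counted from the stop date. The exposure is in participant-level failure classification, resistance and TFV-DP sampling, and the Week 12 or Week 24 RNA value of someone who stops inside a window. This assumes a site acts on 6.6.2 despite 6.6.1 and footnote e. That the visit name is the faulty element is an inference, but the contradiction exists either way.

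The documents give no discontinuation rate on B/F/TAF, so the number affected cannot be stated. A reader might infer that early discontinuers will generally be sampled late, or that the co-primary safety results are compromised. Neither is supported. A visit within 72 hours satisfies every statement. Laboratory results at 3 days or at 30 days after the last dose both fall within the treatment-emergent period; an individual result could differ with timing, but no effect on a co-primary endpoint has been shown.

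**What to change.** Replace the sentence in Section 6.6.2 with: *A participant who is withdrawn from the study will be asked to return for a 30-day follow-up visit within 30 days of stopping study drug, as specified in Table 3 (footnotes c and d).*

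Keep ESDD at 72 hours as in Section 6.6.1 and footnote e. Leave the 30-day limit in footnote d, and make no change to footnote e or to SAP Appendix 1. The cost is one sentence in the protocol, with no new visit, sample or analysis. If the sponsor in fact meant ESDD in 6.6.2, the timing should be corrected to 72 hours instead.

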### **6.7. Sample Storage**

The stored biological samples may be used by Gilead or its research partner for additional testing to provide supplemental data to answer questions that relate to the main study. At the end of this study, these samples may be retained in storage by Gilead for a period up to 15 years or per country requirements if shorter. If participants provide additional specific consent for optional future research, residual biologic samples may be retained in storage no later than 15 years after the end of the study or per country requirements, whichever is shorter (Section [9.1.3](#)).

## 7. ADVERSE EVENTS AND TOXICITY MANAGEMENT

### 7.1. Definitions of Adverse Events and Serious Adverse Events

#### 7.1.1. Adverse Events

An AE is any untoward medical occurrence in a clinical study participant administered a study drug that does not necessarily have a causal relationship with the treatment. An AE can therefore be any unfavorable and/or unintended sign, symptom, or disease temporally associated with the use of a study drug, whether or not the AE is considered related to the study drug. Adverse events may also include pretreatment or posttreatment complications that occur as a result of protocol-specified procedures or special situations (Section 7.1.3).

An AE does not include the following:

- Medical or surgical procedures such as surgery, endoscopy, tooth extraction, or transfusion. The condition that led to the procedure may be an AE and must be reported.
- Preexisting diseases, conditions, or laboratory abnormalities present or detected before the screening visit that do not worsen.
- Situations where an untoward medical occurrence has not occurred (eg, hospitalization for elective surgery, social and/or convenience admissions).
- Overdose without clinical sequelae (Section 7.1.4).
- Any medical condition or clinically significant laboratory abnormality with an onset date before the ICF is signed and not related to a protocol-associated procedure is not an AE but rather considered to be preexisting and should be documented as medical history.

Preexisting events that increase in severity or change in nature after study drug initiation or during or as a consequence of participation in the clinical study will also be considered AEs.

#### 7.1.2. Serious Adverse Events

An SAE is defined as an event that, at any dose, results in the following:

- Death
- A life-threatening situation (Note: the term “life-threatening” in the definition of “serious” refers to an event in which the participant was at risk of death at the time of the event; it does not refer to an event that hypothetically might have caused death if it were more severe.)
- In-patient hospitalization or prolongation of existing hospitalization.

- Persistent or significant disability/incapacity.
- A congenital anomaly/birth defect.
- A medically important event or reaction: such events may not be immediately life-threatening or result in death or hospitalization but may jeopardize the participant or may require intervention to prevent 1 of the other outcomes constituting SAEs. Medical and scientific judgment must be exercised to determine whether such an event is reportable under expedited reporting rules. Examples of medically important events include intensive treatment in an emergency room or at home for allergic bronchospasm; blood dyscrasias or convulsions that do not result in hospitalization; and development of drug dependency or drug abuse.

### **7.1.3.            Serious Adverse Drug Reaction**

A serious adverse drug reaction (SADR) is defined as any SAE that is considered causally related to the medicinal product at any dose administered.

### **7.1.4.            Study Drug and Gilead Concomitant Medications Special Situations Reports**

Special situations reports (SSRs) include all reports of medication error, abuse, misuse, overdose, occupational exposure, drug interactions, exposure via breastfeeding, unexpected benefit, transmission of infectious agents via the product, counterfeit of falsified medicine, and pregnancy regardless of an associated AE.

Medication error is any unintentional error in the prescribing, dispensing, preparation for administration or administration of a study drug while the medication is in the control of a health care professional, participant, or consumer. Medication errors may be classified as a medication error without an AE, which includes situations of missed dose, medication error with an AE, intercepted medication error, or potential medication error.

Abuse is defined as persistent or sporadic intentional excessive use of a study drug by a participant.

Misuse is defined as any intentional and inappropriate use of a study drug that is not in accordance with the protocol instructions or the local prescribing information.

An overdose is defined as an accidental or intentional administration of a quantity of a study drug given per administration or cumulatively that is above the maximum recommended dose as per protocol or in the product labeling (as it applies to the daily dose of the participant in question). In cases of a discrepancy in drug accountability, overdose will be established only when it is clear that the participant has taken the excess dose(s). Overdose cannot be established when the participant cannot account for the discrepancy, except in cases in which the investigator has reason to suspect that the participant has taken the additional dose(s).

Occupational exposure is defined as exposure to a study drug as a result of one's professional or nonprofessional occupation.

Drug interaction is defined as any report of drug/drug, drug/food, drug/alcohol, or drug/device interaction.

Unexpected benefit is defined as an unintended therapeutic effect where the results are judged to be desirable and beneficial.

Transmission of infectious agents is defined as any suspected transmission of an infected agent through a Gilead study drug.

Counterfeit or falsified medicine is defined as any study drug with a false representation of (a) its identity, (b) its source, or (c) its history.

## **7.2. Assessment of Adverse Events and Serious Adverse Events**

The investigator or qualified subinvestigator is responsible for assessing AEs and SAEs for causality and severity, and for final review and confirmation of accuracy of event information and assessments.

### **7.2.1. Assessment of Causality for Study Drug and Procedures**

The investigator or qualified sub-investigator is responsible for assessing the relationship for the study drug using clinical judgment and the following consideration:

- **No:** evidence exists that the AE has an etiology other than the study drug. For SAEs, an alternative causality must be provided (eg, preexisting condition, underlying disease, intercurrent illness, concomitant medication).
- **Yes:** there is reasonable possibility that the AE may have been caused by the study drug.

It should be emphasized that ineffective treatment should not be considered as causally related in the context of AE reporting.

The relationship to study procedures (eg, invasive procedures such as venipuncture or biopsy) should be assessed using the following considerations:

- **No:** evidence exists that the AE has an etiology other than the study procedure.
- **Yes:** the AE occurred as a result of protocol procedures (eg, venipuncture).

### **7.2.2. Assessment of Severity**

The severity of AEs will be graded using the Division of AIDS (DAIDS) Toxicity Grading Scale, Version 2.1. For each episode, the highest grade attained should be reported as defined in the Toxicity Grading Scale (Appendix 11.6).

### **7.3.       Investigator Reporting Requirements and Instructions**

#### **7.3.1.       Requirements for Collection Before Study Drug Initiation**

After informed consent, but before initiation of study drug, the following types of events must be reported on the applicable eCRFs: all SAEs and any AEs that are related to protocol-required procedures.

#### **7.3.2.       Adverse Events**

Following initiation of study drug, collect all AEs, regardless of cause or relationship, until 30 days after administration of the last dose of study drug and report the AEs on the eCRFs as instructed.

All AEs and clinically significant laboratory abnormalities should be followed until resolution or until the AE is stable, if possible. Gilead may request that certain AEs be followed beyond the protocol-defined follow-up period.

#### **7.3.3.       Serious Adverse Events**

All SAEs, regardless of cause or relationship, that occur after the participant first consents to participate in the study (ie, signing the ICF) and throughout the duration of the study, including the 30-day follow-up visit, must be reported on the applicable eCRFs and to Patient Safety (PS) as instructed below in this section. This also includes any SAEs resulting from protocol-associated procedures performed after the ICF is signed.

Any SAEs and deaths that occur after the posttreatment follow-up visit but within 30 days of the last dose of study drug, regardless of causality, should also be reported.

Investigators are not obligated to actively seek SAEs after the protocol-defined follow-up period; however, if the investigator learns of any SAEs that occur after the protocol-defined follow-up period has concluded and the event is deemed relevant to the use of study drug, the investigator should promptly document and report the event to PS.

Instructions for reporting SAEs are described in Section [7.4.1](#).

